9.4.2 Labeling of blood samples

Label tubes with COH protocol #, subject ID (issued by DCC), date and timepoint of collection (e.g. C1D1 for Day1 of Cycle 1), and if applicable patient initials.

9.4.3 Blood collection

Before scheduled blood collection (at least one day in advance) e-mail [name] ([contact]) or [name] ([contact]) at the Analytical Pharmacology Core Facility (APCF) to inform them of a pending collection.

Refer to Table 10 for collection and post-collection instructions.

Note: Collection of blood in Cell-free DNA BCT® (Streck) or purple tubes has priority over the collection of blood in green-top tubes. Also, any heparin in the collection tube of the line used to draw the blood in purple tube will make it unusable.

Table 10. Blood sample collection and post-collection instructions.

Tube Type	Collection details	Site of collection	Post-collection instructions	
			HL and DLBCL patients	FL patients
Green-top	1- Blood samples will be collected from an indwelling venous catheter or by venipuncture. 2- Invert tubes eight times after collection. 3- Immediately place the tubes on ice.	COH	Promptly deliver the blood samples on ice to the APCF, [name] for processing within 4 hours.	Same as for HL and DLBCL patients
Purple-top	Same as for green-top.	COH Only	Promptly deliver the blood samples on ice to the APCF, [name] for processing within 4 hours.	N/A
Cell-free DNA BCT® (Streck)*	1- If applicable, follow recommendations for order of draw outlined in CLSI GP41-A6**. 2- Blood samples will be collected from an indwelling venous catheter or by venipuncture. Prevention of backflow: (Since cell-free DNA BCT® contain chemical additives) a. Keep patient's arm in the downward position during the collection procedure. b. Hold the tube with the stopper in the uppermost position so that the tube contents do not touch the stopper or the end of the needle during sample collection. c. Release tourniquet once blood starts to flow in the tube, or within 2 minutes of application. 3- Fill tube completely. 4- Remove tube from adapter and immediately mix by gentle inversion 8 to 10 times. 5- Do not freeze samples. Store samples at 18-25°C until shipment.	COH	N/A	Ship samples to JAX (see Appendix I). Refer to COH clinical study protocol #17072 for details.

* Tubes are stable when stored at 2-30°C through expiration date. Do not use expired tubes. If there is any indication of cloudiness or visible precipitate immediately contact: (1) For FL patients, [name] or designee ([contact]), any unused/expired blood collection kits should be returned to the Jackson Laboratory Laboratory. (2) For DLBCL and HL patients, contact the COH Data Coordinating Center. Contact information: E-mail: [contact].

** Additional guidelines: Cell-Free DNA BCT should be drawn after the EDTA tube and before the fluoride oxalate (glycolytic inhibitor) tube. If a Cell-Free DNA BCT tube immediately follows a heparin tube in the draw order, Streck recommends collecting a non-additive or EDTA tube as a waste tube prior to collection in the Cell-Free DNA BCT tube.

9.4.4 Sample Processing by APCF (COH)

COH samples only: Blood samples will be kept on a rocker set at low speed to mimic circulation and avoid clot formation until processing.

Green-top tubes (PBMCs AND plasma), for FACS/Cytokine assays:

(Process within 4h of collection for COH samples OR upon receipt of non-COH samples).

- Centrifuge for 10 min at 1800g at 4°C. Both supernatant and pellet will be used.
- Plasma:
 - The resulting upper plasma layer from each tube will be drawn up sequentially into a sterile 5 mL syringe and pushed through a sterile 0.2/0.8 micron disposable filter.
 - The filtered plasma will then be transferred in 500 µL aliquots into multiple appropriately-labeled Starstedt microfuge tubes.
 - To one aliquot, add 0.5 mL glycerol/0.02% sodium azide solution to dilute the plasma 50/50 v/v. Keep the diluted plasma sample at -20°C and do not freeze.
 - All the remaining plasma aliquots will be stored frozen at -80°C until ready for testing.
- PBMCs:
 - Dilute the blood remaining in the green-top tubes used to prepare plasma above 1:1 with Hank's Balanced Salt Solution (or equivalent) in a sterile conical centrifuge tube.
 - Isolate PBMCs by Ficoll-gradient separation per COH APCF procedures.
 - PBMCs samples will be stored in liquid nitrogen until use.

9.5 Laboratory Procedures/Assessments

Details regarding specific laboratory procedures/assessments to be performed in this trial, including laboratory tests for hematology, chemistry, urinalysis, and others are specified in Table 11.

Table 11. Laboratory Tests

Hematology	Chemistry	Urinalysis	Other
Hematocrit	Albumin	Blood	Serum β -human chorionic gonadotropin†
Hemoglobin	Alkaline phosphatase	Glucose	(β -hCG)†
Platelet count	Alanine aminotransferase (ALT)	Protein	PT (INR)
WBC (total and differential)	Aspartate aminotransferase (AST)	Specific gravity	aPTT
Red Blood Cell Count	Lactate dehydrogenase (LDH) (only for DLBCL and FL patients)	Microscopic exam (If abnormal)	Total triiodothyronine (T3)
Absolute Neutrophil Count	Carbon Dioxide ‡	results are noted	Free thyroxine (T4)
Absolute Lymphocyte Count	(CO_2 or bicarbonate)	Urine pregnancy test †	Thyroid stimulating hormone (TSH)
	Uric Acid		
	Calcium		
	Chloride		Blood for correlative studies
	Glucose		
	Phosphorus		
	Potassium		
	Sodium		
	Magnesium		
	Total Bilirubin		
	Direct Bilirubin (If total bilirubin is elevated above the upper limit of normal)		
	Total protein		
	Blood Urea Nitrogen		
	Creatinine		

† Perform on women of childbearing potential only. If urine pregnancy results cannot be confirmed as negative, a serum pregnancy test will be required.

‡ If considered standard of care in your region.

After Cycle 1, pre-dose laboratory procedures can be conducted up to 72 hours prior to dosing. Results must be reviewed by the investigator or qualified designee and found to be acceptable prior to each dose of trial treatment.

9.5.1 Correlative Studies

A non-exhaustive list of correlative studies is provided in Section 4.6.5 “Rationale for Biomarker Research”.

Correlative studies will mainly be performed in the laboratories of [name], Chair of the City of Hope Beckman Research Institute Division of Cancer Immunotherapeutics and Tumor Immunology, and [name], Professor of Pathology at City of Hope Medical Center.

For FL patients only, some tumor and blood samples will be analyzed at the Jackson Laboratory (ctDNA studies) (see COH clinical study protocol #17072).

9.5.2 Other Procedures

9.5.2.1 Withdrawal/Discontinuation

When a subject discontinues/withdraws prior to trial completion, all applicable activities scheduled for the final trial visit should be performed at the time of discontinuation. Any adverse events that are present at the time of discontinuation/withdrawal should be followed in accordance with the safety requirements outlined in Section 9.2. Subjects who a) attain a CR or b) complete 24 months of treatment with pembrolizumab may discontinue treatment. After discontinuing treatment following assessment of CR or completing 24 months of treatment, these subjects should return to the site for a Safety Follow-up Visit and then proceed to the Follow-Up Period of the study.

9.5.3 Visit Requirements

Visit requirements are outlined in Section 8.0 - Trial Flow Chart. Specific procedure-related details are provided above in Section 9.0 - Trial Procedures.

9.5.3.1 Screening Period

The following procedures will be performed during Screening:

- Informed Consent
- Review of eligibility criteria (Inclusion/Exclusion criteria)
- Medical history and demographics
- Review of prior and concomitant medications

- Complete physical exam
- Vital signs, weight and height, and oxygen saturation
- ECOG Performance Status
- 12-lead ECG
- Bone marrow aspirate and biopsy (Not for all patients: refer to study calendar and footnote j).
- Collection of tumor tissue from fresh tumor biopsy or archival specimen
- PET-CT (DLBCL, HL, FL) or IV contrast-enhanced CT scan of neck, chest, abdomen, pelvis of diagnostic quality (only FL). MRI can be used for lesions not well-visualized by CT, or if CT with IV contrast is contraindicated. See sections 9.2.6 and 10.1 for additional details.
- Clinical laboratory tests for:
 - Hematology
 - Serum chemistry
 - Coagulation (PT, PTT, INR)
 - Serum or urine pregnancy test (for women of childbearing potential who have not been free from menses for > 1 year). Should be performed within 72 hours prior to first dose of therapy.
 - Urinalysis

9.5.3.2 Treatment Period

The following procedures will be performed during the treatment period:

NOTE: This is a list of procedures. Not all procedures will necessarily be performed at each cycle.

- Complete physical exam
- ECOG Performance Status
- Vital signs and weight

- Buccal swab
- 12-lead ECG
- Clinical laboratory tests for:
 - Hematology
 - Serum chemistry
 - Thyroid function panel
 - Serum or urine pregnancy test (for women of childbearing potential who have not been free from menses for > 1 year).
- Review of AEs
- Research laboratory blood samples collected pre-dose for correlative studies (See section 9.4 for additional details).
- PET-CT or IV contrast-enhanced CT scan of neck, chest, abdomen, pelvis of diagnostic quality. See sections 9.2.6 and 10.1 for additional details.
- To be completed to confirm CR:
 - PET scan (if only CT scan was used for response assessment)
 - Bone marrow aspirate and biopsy (if bone marrow was involved at baseline)
- Dosing
 - Dispense vorinostat and diary card
 - In-clinic administration of vorinostat
 - In-clinic administration of pembrolizumab (after vorinostat administration)

9.5.3.3 Post-Treatment Visits

9.5.3.3.1 Safety Follow-Up Visit

The mandatory Safety Follow-Up Visit should be conducted 30 days after the last dose of trial treatment or before the initiation of a new anti-cancer treatment, whichever comes first. Subjects with an AE of Grade > 1 will be followed until the resolution of the AE to Grade 0-1

or until the beginning of a new anti-neoplastic therapy, whichever occurs first. SAEs that occur within 90 days of the end of treatment or before initiation of a new anti-cancer treatment should also be followed and recorded.

9.5.3.4 Follow-up Visits

Subjects who discontinue trial treatment for a reason other than disease progression will move into the Follow-Up Phase and should be assessed every 12 weeks (84 ± 7 days) by radiologic imaging to monitor disease status. After 1 year, the imaging time point will occur every 18 weeks (± 7 days). Every effort should be made to collect information regarding disease status until the start of new anti-neoplastic therapy, disease progression, death, and end of the study. Information regarding post-study anti-neoplastic treatment will be collected if new treatment is initiated.

9.5.3.4.1 Survival Follow-up

Once a subject experiences confirmed disease progression or starts a new anti-cancer therapy, the subject moves into the survival follow-up phase and will be followed for survival status until death, withdrawal of consent, or the end of the study, whichever occurs first. Survival assessment to occur bi-annually or as requested by the Study PI via medical record review, review of social security registry, or telephone call.

10.0 ENDPOINT EVALUATION CRITERIA/MEASUREMENT OF EFFECT

10.1 Response Criteria

Disease response/progression will be evaluated using 2014 Lugano Classification (see Appendix C)^{122, 139}. Participants who meet the definition of progressive disease per Lugano Classification should be evaluated using the LYRIC criteria (see Appendix L).

For all patients:

- Disease staging will be performed every 4 cycles until disease progression or off study therapy.
- Disease assessment will be performed either by PET-CT (FDG-avid histologies) or diagnostic quality CT of the neck, chest, abdomen and pelvis (N/C/A/P) with IV contrast (see restrictions below).
- MRI may be performed at the investigator's discretion for lesions not well-visualized by CT, or if CT with intravenous contrast is contraindicated.
- Whenever a PET-CT is not performed, a diagnostic quality (N/C/A/P) CT with IV contrast must be performed instead.

Note: if there is no evidence of neck involvement by lymphoma at baseline, CT of chest, abdomen and pelvis (C/A/P) can be performed instead of N/C/A/P at subsequent re-staging.

For DLBCL and HL patients only:

- Disease assessment requires a PET-CT be performed at baseline (within the screening window) and at cycle 4 (Day 15-21 [-3 days]).
- Although not required, it is recommended that DLBCL and HL patients who are not in CR get a PET-CT at least every 8 cycles thereafter, and every 24 weeks for patients who discontinued for other reasons than CR.
- Assessment with PET-CT is required to confirm CR. Once CR has been confirmed, diagnostic quality (N/C/A/P) CT with IV contrast can be used instead of PET-CT until progression, unless otherwise specified below.
Note: if there is no evidence of neck involvement by lymphoma at baseline, CT of chest, abdomen and pelvis (C/A/P) can be performed instead of N/C/A/P at subsequent re-staging.

For FL patients only:

- Disease assessment by diagnostic quality (N/C/A/P) CT with IV contrast or PET-CT is allowed at any time point.
Note: if there is no evidence of neck involvement by lymphoma at baseline, CT of chest, abdomen and pelvis (C/A/P) can be performed instead of N/C/A/P at subsequent re-staging.

PET-CT and CT results will be read by radiology at each study site and investigator response based on radiology reading will be performed. Lymphoma response assessment based on PET-CT/CT will be based on the 2014 Lugano Classification (Appendix C).¹³⁹

Unless clinically indicated, bone marrow aspirate and biopsy will be performed only to confirm CR and only in patients with bone marrow involvement at study enrollment.

For patients with progression of disease on imaging, it is strongly recommended that a confirmatory biopsy be obtained whenever possible. Note that an FDG-negative PET scan will only be considered complete remission in patients whose tumor was FDG-avid at baseline.

As a secondary endpoint, we will evaluate the LYRIC refinement of the Lugano classification (Appendix L), which is specifically aimed at improving response evaluation in lymphoma immunotherapy clinical trials.²⁸

10.2 Endpoint Definitions

Overall Response Rate (ORR): Defined as the proportion of patients that have a documented CR or PR at any time during study treatment.

Complete Response (CR) rate: Defined as the proportion of patients that have a documented CR at any time during study treatment.

Duration of Response (DOR): Defined as the time from the first achievement of PR or CR to time of PD. Patients who never achieve PR or CR are excluded. Patient who has not had disease progression/relapse at last follow-up is censored at the time of last follow-up. If a patient receives non-protocol anti-lymphoma treatment prior to disease progression, the patient is censored at the time of non-protocol anti-lymphoma treatment.

Overall Survival: Defined as time from initiation of study therapy to death from any cause. If a patient is alive at the last evaluation time period, survival time is censored at the time of last follow-up.

Progression-Free Survival (PFS): Defined as the time from initiation of study therapy to the first observation of disease relapse/progression or death from any cause, whichever occurs first. If the patient has not progressed relapsed or died, the patient is censored at the time of last follow-up. If a patient receives non-protocol anti-lymphoma treatment prior to disease progression, the patient is censored at the time of non-protocol anti-lymphoma treatment.

Toxicity: Toxicity and adverse events will be recorded using the NCI CTCAE 4.03 scale. Observed toxicities will be summarized by type (organ affected or laboratory determination such as absolute neutrophil count), severity (by NCI CTCAE v4.03 and nadir or maximum values for lab measures), date of onset, duration, reversibility, and attribution.

Unacceptable Toxicity: defined as one of the following AEs that is at least possibly related to study treatment, at any point on study therapy:

- Any Gr 3 or higher IrAE that does not resolve to Gr ≤ 1 within 7 days with the exception of:
 - Grade 3 immune-related hepatitis if ALT or AST $< 8 \times$ ULN or total bilirubin $< 5 \times$ ULN.
 - Grade 3 asymptomatic endocrinopathy.
 - Local inflammatory response to study therapy.
- Any other Gr ≥ 4 AE with the exception of:
 - Non-clinically significant laboratory abnormalities
 - Local inflammatory response to study therapy.
- Any Gr 5 AE.

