7.12 Subject Withdrawal/Discontinuation Criteria

Subjects may withdraw consent at any time for any reason or be dropped from the trial at the discretion of the investigator should any untoward effect occur. In addition, a subject may be withdrawn by the investigator or the Sponsor if enrollment into the trial is inappropriate, the trial plan is violated, or for administrative and/or other safety reasons. Specific details regarding discontinuation or withdrawal are provided in Section 9.5.2 - Other Procedures.

A subject must be discontinued from the trial for any of the following reasons:

- The subject or legal representative (such as a parent or legal guardian) withdraws consent.
- Confirmed radiographic disease progression

Note: A subject may be granted an exception to continue on treatment with confirmed radiographic progression if clinically stable or clinically improved, please see Section 9.5.3.5

- Unacceptable adverse experiences, either DLT (Section 7.2) or other unacceptable toxicity (Section 10.2).
- Intercurrent illness that prevents further administration of treatment

- Investigator's decision to withdraw the subject
- The subject has a confirmed positive serum pregnancy test
- Noncompliance with trial treatment or procedure requirements
- The subject is lost to follow-up
- Completed 24 months of uninterrupted treatment with pembrolizumab or 35 administrations of study pembrolizumab, whichever is later.

Note: 24 months of study medication is calculated from the date of first dose.

- Administrative reasons

The End of Treatment and Follow-up visit procedures are listed in Section 8 (Protocol Flow Chart) and Section 9.5.3 (Visit Requirements). After the end of treatment, each subject will be followed for 30 days for adverse event monitoring (serious adverse events will be collected for 90 days after the end of treatment). Subjects who discontinue for reasons other than progressive disease will have post-treatment follow-up for disease status until disease progression, initiating a non-study cancer treatment, withdrawing consent or becoming lost to follow-up. After documented disease progression each subject will be followed for overall survival until death, withdrawal of consent, or the end of the study (last patient off therapy), whichever occurs first.

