9.2.6.1 Disease Progression Assessments

Response patterns observed with immunotherapeutic agents such as pembrolizumab may extend beyond the typical time course of responses seen with cytotoxic agents, and can manifest a clinical response after an initial increase in tumor burden or even the appearance of new lesions. Standard response criteria may not provide a complete response assessment of immunotherapeutic agents like pembrolizumab. Therefore, at a scheduled disease assessment, if the assessment demonstrates PD, the study regimen may be continued, at the discretion of the principal investigator, until the next disease response assessment provided that the subject's clinical condition is stable and the conditions below are met. However, imaging should occur at any time where there is clinical suspicion of progression.

Subjects may continue to receive treatment in the event of progressive disease if the following criteria are met:

- Absence of signs or symptoms (including worsening of laboratory values) indicating disease progression.
- No decline in ECOG performance status.
- Absence of rapid progression of disease
- Absence of progressive tumor at critical anatomical sites (e.g. spinal cord compression) requiring urgent alternative medical intervention.

At disease response assessments beyond the initial assessment, the Investigator, in consultation with the Principal Investigator, may keep a clinically stable subject on study treatment as long as the subject meets the above criteria and is deriving clinical benefit.

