11.1.3 Analysis of Anti-tumor Activity

This study will aim to obtain preliminary estimates of the anti-tumor activity of the study combination. ORR will be calculated as the proportion of evaluable patients that have confirmed CR or PR, as defined according to the 2014 Lugano Classification, exact 95% confidence intervals will be calculated for these estimates. Response rates will also be evaluated based on number and type of prior therapy(ies). Time to response, duration of response, as well as progression-free survival and overall survival will be estimated using the product-limit method of Kaplan and Meier.

These efficacy analyses will be performed separately for DLBCL, FL, and HL patients. Any patient treated at the RP2D, including those from the dose-escalation cohort, will be included in efficacy analyses. Patients will be evaluable for efficacy assessment if they received at least one dose of vorinostat and one dose of pembrolizumab and underwent at least one response assessment. Patients will be evaluable for efficacy if they discontinued study therapy prior to the first response assessment because of progression of disease rather than solely because of unacceptable toxicity, withdrawal of consent, or investigator decision. If a patient discontinues study treatment prior to the first response assessment due to progressive disease, the treating physician is encouraged to obtain imaging to confirm progression.

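### ORR and CR rate are bounded only by study treatment, so responses read after Lugano PD are not excluded, and Sections 10.2 and 11.1.3 disagree on responses first seen after stopping

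*Combined protocol and SAP*

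**What the plan says.** **Response window.** Section 10.2 gives ORR as "Defined as the proportion of patients that have a documented CR or PR at any time during study treatment" and CR rate as "Defined as the proportion of patients that have a documented CR at any time during study treatment". Neither definition ends at progression or at new therapy.

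**Analysis text.** Section 11.1.3 states: "ORR will be calculated as the proportion of evaluable patients that have confirmed CR or PR, as defined according to the 2014 Lugano Classification". It gives no time window, and it uses *confirmed* where Section 10.2 uses *documented*.

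**Linked endpoints.** Section 10.2 gives DOR as "Defined as the time from the first achievement of PR or CR to time of PD". PFS takes the first observed progression, or death, as its event. Both are censored at non-protocol anti-lymphoma treatment.

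**Treatment after PD.** Section 9.2.6.1 says that "if the assessment demonstrates PD, the study regimen may be continued, at the discretion of the principal investigator, until the next disease response assessment", subject to clinical conditions, and it allows continuation at later assessments too. Its reason is that response patterns under immunotherapy "can manifest a clinical response after an initial increase in tumor burden or even the appearance of new lesions". A note in Section 7.12 adds: "A subject may be granted an exception to continue on treatment with confirmed radiographic progression if clinically stable or clinically improved". Appendix L keeps patients with an indeterminate response on therapy and repeats imaging after a further 12 weeks.

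**LYRIC.** Sections 9.2.6 and 10.1 direct patients who meet Lugano PD to evaluation by LYRIC. Appendix L makes LYRIC CR and PR identical to Lugano; only the progression category differs.

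**After stopping.** Section 9.5.3.4: "Subjects who discontinue trial treatment for a reason other than disease progression will move into the Follow-Up Phase", with imaging every 12 weeks and, after a year, every 18 weeks. Section 10.1 recommends, but does not require, PET-CT every 24 weeks for DLBCL and HL patients who stopped for reasons other than CR.

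**The concern.** A response rate, a response duration and a PFS curve reported from one trial should describe the same disease course. Here the response window follows drug exposure, whereas PFS and DOR follow progression. Because treatment can outlast Lugano PD, one patient can be a PFS failure and then an ORR responder.

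This also blurs the LYRIC analysis. Since CR and PR are the same under both criteria, the LYRIC response rate can differ from the Lugano rate only through responses read after Lugano PD. If the Lugano ORR already counts those, the two rates largely coincide and the comparison says little.

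In the other direction, Section 10.2 read alone leaves out a first response seen in follow-up, while Section 11.1.3 read alone admits it. Two analysts following the same document could report different rates.

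**Working it through.** No stated figure depends on this definition. The expected sample size reproduces (12 + 40 = 52), but the plan gives no target ORR, power or precision goal. The check is therefore mainly a reading of the sections against two hypothetical patients.

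**Scan timing.** Staging is every 4 cycles of 21 days: 4 × 21 / 7 = 12 weeks, so scans fall near weeks 12, 24 and 36.

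**Patient A:** SD at week 12, Lugano PD at week 24, kept on treatment, PR at week 36.

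**Patient B:** SD at week 12, stops both drugs without PD, first PR on a follow-up scan, no new therapy.

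| | Patient A | Patient B |
|---|---|---|
| PFS | Event at week 24 | No event yet |
| ORR by Section 10.2 | Responder | Not a responder |
| ORR by Section 11.1.3 | Not excluded, if confirmed | Responder, if confirmed |
| DOR | PD precedes response: 24 − 36 = −12 weeks | Can enter; DOR has no on-treatment limit |

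For Patient A, taking a later second PD as the DOR event would give a positive number, but for a response that lies wholly after the PFS event. Such a PR can be read: Appendix C judges metabolic PR by uptake relative to baseline, with no new lesions present. An increase that later reverses can therefore meet it. A patient who had already responded before PD does not change ORR, but a first CR after PD could still change the CR rate.

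For Patient B, the CR-rate analogue is a patient with PR on treatment whose first CR is read in follow-up.

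**Size, by assumption.** The number of affected patients is not in the documents, so assume one (or two). Each reclassified patient moves ORR by 100/n points:

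- n = 10 (the added HL patients, Section 4.6.4): 100/10 = 10 points
- n = 15 (the previously PD-1-exposed patients, Section 4.6.4): 100/15 = 6.7 points
- n = 25 (15 + 10, if pooled): 100/25 = 4 points

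Exact 95% limits for x responders in n are the 0.025 quantile of Beta(x, n − x + 1) and the 0.975 quantile of Beta(x + 1, n − x):

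- 13/15, the count in Section 4.6.4: 86.7% (59.5 to 98.3)
- one fewer, 12/15: 80.0% (51.9 to 95.7); two fewer, 11/15: 73.3% (44.9 to 92.2)
- one more, 14/15: 93.3% (68.1 to 99.8)
- invented counts in 10 patients: 5/10 = 50.0% (18.7 to 81.3) against 6/10 = 60.0% (26.2 to 87.8)

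**The case against.** **The plan does not say that post-PD responses count.** Sections 9.2.6 and 10.1 run staging until progression or the end of study therapy and then turn to LYRIC, and the DOR wording presumes that PD follows response. A reader might infer that the plan prescribes counting post-PD responses in the Lugano ORR. It does not; it fails to exclude them. That limit stands. It does not close the gap, because Section 9.2.6.1 and Appendix L provide for imaging after PD, and no section, including 11.1.3, removes such a response from the numerator.

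**The off-treatment loss is narrow.** A reader might infer that any patient who stops for toxicity and later responds is scored a non-responder. The documents do not support that:
- Section 7.4 replaces expansion patients who stop before the first assessment for reasons other than PD.
- Section 11.1.3 describes patients who stop that early solely for toxicity as outside the evaluable set, although its separate requirement of one or more response assessments leaves some ambiguity if a later scan exists.
- Stopping one drug need not end study treatment, since Sections 7.6.1.2 and 7.7.1 let the other continue.

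What clearly remains is Patient B.

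**An on-treatment window is a defensible choice.** It ties response to exposure and to scheduled scans. This is fair. The fault in this half is that the two sections differ, not that either choice is wrong.

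**The size is hypothetical.** This is also fair. The 10 added patients are not a named efficacy stratum: Section 11.1.3 analyses by histology and also looks at number and type of prior therapy. The illustrative intervals overlap almost entirely.

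**Conclusion.** The point holds as a defect of definition. Read literally, the Section 10.2 window lets a patient with a PFS event at first Lugano PD become a Lugano responder whose DOR has no valid start, and no other section prevents it. Separately, Sections 10.2 and 11.1.3 disagree on whether a first response after stopping both drugs, before PD or new therapy, counts. For ORR this affects only patients with a non-response on an on-treatment scan who then stop both drugs.

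On the assumption of one reclassified patient, ORR moves by 10 points in 10 patients, about 7 in 15, or 4 in 25. ORR is a secondary endpoint estimated descriptively, so alpha, power, sample size and decision thresholds are untouched. A reader might also infer that the 13 responses among 15 patients in Section 4.6.4 are inflated. The documents do not say when those responses fell relative to PD, so that inference has no support.

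**What to change.** In Sections 10.2 and 11.1.3 alike, and in the matching text of the Trial Summary:

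1. Define ORR and CR rate as best Lugano response from first dose to the earlier of first Lugano PD or the start of non-protocol anti-lymphoma therapy.
2. Start DOR only from a response inside that window.
3. Report responses after Lugano PD under LYRIC only.
4. State one rule for responses first seen off treatment but before PD or new therapy. If they are counted, also report them separately.
5. Use either *confirmed* or *documented* in both places, and define the term.

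The cost is a few sentences of text. The change uses data already planned and alters no treatment rule. There is one small downside: off-treatment PET-CT is only recommended for DLBCL and HL, while PET-CT is required to confirm CR. CR ascertainment after stopping will therefore be uneven, which is why those responses need their own line.
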